## Study Design

Describe and explain the study design (e.g., observational, secondary analysis, single/double blind, parallel, crossover, deception, etc.).

- **Clinical Research:** Indicate whether subjects will be randomized and whether subjects will receive any placebo.
- **Community-Based Participatory Research:** If you are conducting [community-based participatory research \(CBPR\)](#), describe strategies for involvement of community members in the design and implementation of the study, and dissemination of results from the study.
- **Qualitative research:** Indicate ranges where flexibility is needed, if a fixed interview transcript is not available, describe interview topics including the most sensitive potential questions.
- **Research Repositories:** If the purpose of this submission is to establish a Research Repository (bank, registry) and the material you plan to collect is already available from a commercial supplier, clinical lab, or established IRB approved research repository, provide scientific justification for establishing an additional repository collecting duplicate material. Describe the repository design and operating procedures. For relevant information to include, see the [UK Research Biospecimen Bank Guidance](#) or the [UK Research Registry Guidance](#).

This will be a within participant single blinded trial. Recruitment for the study will be done by research assistant and/or principal investigator. All study participants will receive active cTBS first and sham cTBS stimulation one week later. Although participants will be blinded to the intervention, the PI ([name]) and his research assistant will not be blind to the intervention and will deliver the sessions. We will recruit 30 subjects who will receive both active and sham cTBS.

On day one of the study, we will perform baseline assessments including breath alcohol level, alcohol attentional bias tasks using eye tracker, and collection of baseline demographics. All of these baseline assessments will take a total of three hours. We will also obtain resting and active motor threshold from the first dorsal interosseous (FDI) muscle. Following this subjects will be transported to Magnetic Resonance Imaging and Spectroscopy Center (MRISC), affiliated with University of Kentucky for collection of their baseline MRI brain scan that will last thirty minutes. A study team member will escort them to the MRISC and will be with them when the scan is obtained.

On day two of the study all study participants will receive active stimulation which is two sessions of continuous theta burst stimulation (cTBS) to the left dorsolateral prefrontal cortex. Both sessions will be separated by 50 minutes. Participants will perform the alcohol craving scale, AUDIT-C and attentional bias for alcohol cues before and after the two cTBS sessions. The same sequence of events will occur on day three of the study, but all participants will receive sham cTBS. We will acquire functional MRI (fMRI) scan on both study days 2 and 3, after the active cTBS sessions and sham cTBS session respectively. Study days 2 and 3 will be separated by a week.

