## Objectives

List your research objectives. Please include a summary of intended research objectives in the box below.

To demonstrate whether two sessions of continuous TBS (cTBS) decreases attentional bias for alcohol cues, alcohol craving and changes resting state functional connectivity in people with alcohol use disorder (AUD) compared to two sessions of sham cTBS. We hypothesize 2 sessions of cTBS to the left dorsolateral prefrontal cortex (L. dlPFC) will significantly decrease attentional bias for alcohol cues, alcohol craving and change resting state functional connectivity in a population of people with AUD compared to sham cTBS.

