**Research Procedures**

Describe how the research will be conducted.

- What experience will study participants have?
- What will study participants be expected to do?
- How long will the study last?
- Outline the schedule and timing of study procedures.
- Provide visit-by-visit listing of all procedures that will take place.
- Identify all procedures that will be carried out with each group of participants.
- Describe deception and debrief procedures if deception is involved.

Differentiate between procedures that involve standard/routine clinical care and those that will be performed specifically for this research project. List medications that are explicitly forbidden or permitted during study participation.

On day one of the study, following informed consent, we will perform baseline assessments including breath alcohol level, alcohol craving questionnaire, alcohol attentional bias tasks using eye tracker, and collection of baseline demographics. All of these baseline assessments will take a total of three hours. We will evaluate for any contraindications for MRI using the MRI checklist (attached). We will also obtain resting and active motor threshold from the first dorsal interosseous (FDI) muscle. Following this subjects will be transported to Magnetic Resonance Imaging and Spectroscopy Center (MRISC), affiliated with University of Kentucky for collection of their baseline MRI brain scan that will last thirty minutes. A study team member will escort them to the MRISC and will be with them when the scan is obtained.

On the second day, subjects will receive two sessions of active cTBS. Sessions will be the same in dosing and will be delivered at an interval of fifty minutes. Each session will last five minutes regardless of it being cTBS or sham cTBS. Active cTBS sessions will be delivered 120% resting motor threshold (RMT) to the left dorsolateral prefrontal cortex using a figure 8 coil and MagVenture MagPro x100 device (MagVenture A/S, Denmark), with TMS coil position stabilized using BrainSight (Rogue Solutions, Montreal, Canada). Subjects will also perform a host of other tasks as shown in figure 1 before and after the two cTBS sessions. At the end of the cTBS sessions and tasks, post session MRI brain scan will be collected at MRISC.

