On day three of the study, participants will receive two sessions of sham cTBS. The sham cTBS mimics the actual experimental one but does not deliver any electricity to the brain. The sham sessions will be separated by 50 minutes. Participants will perform a host of other tasks as shown in figure 1 before and after the two sham cTBS sessions. At the end of day three, we will have participants undergo an MRI brain scan at MRISC.

A medical doctor will be present or nearby during all stimulation sessions. No drug, pregnancy, etc. screening results will be obtained from a UK HealthCare laboratory.

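### Every participant gets active cTBS first and sham a week later, so the planned t-test supports the comparison with sham only under unstated assumptions about order and carryover

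*Combined protocol and SAP*

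**What the plan says.** The Objectives section sets a comparative aim: the effect of two active sessions on attentional bias, craving and resting-state connectivity "in people with alcohol use disorder (AUD) compared to two sessions of sham cTBS".

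The order is the same for everyone. Study Design says: "All study participants will receive active cTBS first and sham cTBS stimulation one week later". On the sham day, "The same sequence of events will occur on day three of the study, but all participants will receive sham cTBS". Research Procedures agrees: "On day three of the study, participants will receive two sessions of sham cTBS". No section gives a second sequence, a parallel control, a reason for the order or a rationale for the one-week interval.

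On each stimulation day participants complete the craving scale, AUDIT-C and "attentional bias for alcohol cues before and after the two cTBS sessions". Imaging is different: "We will acquire functional MRI (fMRI) scan on both study days 2 and 3, after the active cTBS sessions and sham cTBS session respectively". Those two days have no pre-stimulation scan.

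The Statistical analysis plan summarises craving and attentional bias at a baseline and after the second session, for both conditions, and compares the changes with t-tests. It does not define baseline, does not say whether the test is paired, and has no period term or statement about order or carryover.

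**The concern.** With a single sequence, anything that makes the Day 2 response differ from the Day 3 response is attributed to cTBS. Candidates are task practice, habituation, expectancy on the first stimulation day and floor effects. An order effect could create a difference or hide one, and a p-value reported without this limit would read as evidence against sham.

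The timing adds to the problem. Subject Info To-Date gives 8 enrolled of 30 approved, and Progress of the Research says that only data analysis remains, so the design cannot be repaired. The continuation review already records reduced craving as a benefit. Study Design says that the principal investigator and "his research assistant will not be blind to the intervention and will deliver the sessions". Any clarification of the analysis made now is therefore post hoc and should say so.

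**Working it through.** The plan gives no sample-size calculation, alpha, effect size or SD, so there is no figure of its own to reproduce.

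**1. Can treatment and visit be separated?** Take each participant's Day 2 minus Day 3 difference. The treatment coefficient is 1 for everyone and the period coefficient is 1 for everyone. The two columns are identical (rank 1 of 2), so no model fitted to these data alone separates them. With half the participants in the reverse order, the rank is 2.

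**2. What enters the contrast?** Let τ be the effect of active over sham, L2 and L3 the pre-session levels without carryover, w2 and w3 the within-day changes that would occur anyway, and c and c′ the carryover present at the Day 3 pre- and post-session assessments.

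- Same-day baseline: (Day 2 post − pre) − (Day 3 post − pre) = τ + (w2 − w3) + (c − c′).
- Day 1 baseline: the Day 1 value drops out, leaving Day 2 post − Day 3 post = τ + (L2 − L3) + (w2 − w3) − c′.

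An example in arbitrary units, with τ = −1.0 and negative meaning a decrease:

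| Departure | Same-day baseline | Day 1 baseline |
|---|---|---|
| Downward trend, 0.25 per assessment | −1.0 | −1.0 + 0.5 = −0.5 |
| Day 3 level lower by 0.5 | −1.0 | −0.5 |
| Stable carryover of 50% | −1.0 | −0.5 |
| Extra within-day decrease of 0.5 on Day 2 only | −1.5 | −1.5 |

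On the same-day reading only the last row biases the result. If τ were zero, that row would give −0.5. A direct comparison of the Day 2 and Day 3 scans has no same-day baseline, so level shifts and carryover enter it too: −0.5 for either the 0.5 level shift or the 50% carryover, and −0.75 for the trend, because the scans are one assessment apart.

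**3. Does decay of carryover within Day 3 matter?** Assume that 50% of the effect remains after one week (168 hours), that decay is exponential, and that the two Day 3 assessments are 1 to 6 hours apart. The residual falls from 50% to 50% × 2^(−1/168) = 49.8%, or to 50% × 2^(−6/168) = 48.8%. Then c − c′ is about 0.002 to 0.012 of the effect, which is negligible.

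**4. How large could the error be?** Assumptions, none from the documents: no true effect, a paired t-test, two-sided 5%, and an order effect d in SDs of the paired difference. The rejection rate is P(|T| > t(0.975, n−1)), with T noncentral t and noncentrality d√n.

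| d | n = 8 (d√n) | n = 30 (d√n) |
|---|---|---|
| 0.2 | 7.8% (0.566) | 18.5% (1.095) |
| 0.5 | 23.2% (1.414) | 75.4% (2.739) |
| 0.8 | 49.6% (2.263) | 98.8% (4.382) |

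Masking works the same way: a true effect of 0.5 SD opposed by an order effect of 0.3 SD leaves 0.2 SD, and at n = 30 the rejection rate falls from 75.4% to 18.5%. An unpaired test on the same data, with an assumed correlation of 0.7 to 0.3 between the two days' changes, would reject less often at n = 8: about 1–4%, 3–16% and 12–41% (simulated). The bias in the estimate would be unchanged.

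**5. Would randomised order have helped?** In simulation with randomised order and a period adjustment, type I error stays between 4.9% and 5.0% for order effects from 0 to 0.8 SD, at both sample sizes. Power is P(|T| > t(0.975, n−2)) with the same noncentrality: 75.3% against 75.4% at n = 30 and 0.5 SD, and 47.6% against 49.6% at n = 8 and 0.8 SD.

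**The case against.** The best defence is that the plan compares changes and that craving and attentional bias are measured before and after stimulation on each day. On that reading much of what is usually feared from a fixed order cancels. This stands, and it narrows the concern to the term w2 − w3.

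The same-day reading is also the better one. The SAP takes its two time points in each condition, which implies a baseline for each. Research Procedures does say of Day 1 that "we will perform baseline assessments including breath alcohol level, alcohol craving questionnaire, alcohol attentional bias tasks using eye tracker", but the Day 1 list in Study Design omits craving, so a Day 1 craving baseline is not consistently documented. Figure 1 is not available here. It might settle the baseline, but not the order, which the text states repeatedly.

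Day 2 is not the first exposure either. Participants have already done the attentional bias task and received TMS pulses for the motor threshold on Day 1. This may blunt practice and novelty, but nothing in the documents shows that it removes them.

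The protocol discloses the order and never claims randomisation, and the rates for 30 participants describe a study that will not now take place. Both points are fair. Neither supplies the missing assumptions.

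A reader might infer that carryover inflates the same-day contrast. A material bias would need much of a one-week residual to vanish within hours, which is not credible. A reader might also take the Background's report of connectivity changes 2 and 3 months after cTBS as proof of carryover here. That study gave ten sessions at a different target, so it shows a possibility only.

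**Conclusion.** The concern holds in limited form, and it should be fixed because it determines what the trial can conclude. The order is fixed, treatment is confounded with visit, and the t-test supports the stated objective only if there is no order effect on the within-day change and no material carryover. These data can test neither assumption.

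On the same-day baseline the live threat is a visit-specific difference in the within-day change. If baseline meant Day 1, or if the Day 2 and Day 3 scans were compared directly, order and carryover would enter in full.

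The confounding follows from the design and does not depend on any assumed size. The 8%, 23% and 50% false-rejection rates for 8 participants do: they rest on assumed order effects of 0.2 to 0.8 SD, a paired test and all 8 being analysed.

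It would be tempting to say that the comparison is no evidence at all. The documents do not support that. A fixed-order comparison with sham is weak evidence that depends on assumptions, and it cannot establish the objective by itself.

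**What to change.** Leave the protocol's Objectives section unchanged. Add to the SAP, dated and labelled post hoc:

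> Change is the post-second-session value minus the same-day pre-session value. Active-day and sham-day changes are compared with a paired t-test, and each day's n and mean change with 95% CI are reported. All participants received active first and sham one week later, so this is a non-randomised, fixed-order comparison confounded with visit. Reading the difference as an effect of cTBS compared with sham assumes no order effect on within-day change and no material carryover, which these data cannot test. The comparison is exploratory and cannot by itself establish the stated objective.

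State the same limit for any direct comparison of the Day 2 and Day 3 scans, where order and carryover enter in full. Do not use a Day 1 baseline as a robustness check. If it is reported, say that it is more exposed to both.

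Only if the study is extended or repeated: randomise the order 1:1, analyse with treatment and period terms, and justify the interval between visits, because randomised order does not remove carryover. This needs a randomisation list and one degree of freedom, and power is almost unchanged.

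The clarification needs no new data. Its real cost is that a causal conclusion against sham is given up for the data already collected. What remains is also imprecise: if all 8 completed, each day's mean change has a 95% CI of about ± t(0.975, 7)/√8 = 0.84 SD of that day's change.

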## Attachments

### Subject Recruitment Methods & Advertising

Describe how the study team will identify and recruit subjects. Please consider the following items and provide additional information as needed so that the IRB can follow each step of the recruitment process.

- How will the study team identify potential participants?
- Who will first contact the potential subjects, and how?
- Will you use advertisements? If so, how will you distribute those?
- How and where will the research team meet with potential participants?
- If applicable, describe proposed outreach programs for recruiting women, minorities, or disparate populations.
- How will minimize undue influence in recruitment?
- Attach copies of all recruiting and advertising materials (emails, verbal scripts, flyers, posts, messages, etc.).

For additional information on recruiting and advertising:

- [IRB Application Instructions - Advertisements](#)
- [PI Guide to Identification and Recruitment of Human Subjects for Research](#)

We will recruit 30 subjects from the various clinics within the University of Kentucky Medical Center including our clinics at [name]. All providers in the clinics at [name] will be provided multiple copies of the study flyer. Study members will interface with all providers in the clinic at [name] on a daily basis. We will provide copies of the flyer to other clinics (Turfland, Team blue,

Polk Dalton clinic) and referrals if any from these clinics will be scheduled for visit one if they fit our inclusion and exclusion criteria and are interested in the study.

[name] will approach her patients who meet study criteria and ask about interest in participation. [name] will serve as the medical screener for inclusion/exclusion appropriateness. Patients who are interested in participation will be referred to the study staff for more information.

Participants interested in the study can call the number provided on the flyer to express interest in the study. Once they express interest, participants will be scheduled for the first visit. Initial contact will be made with potential subjects by those having legitimate access to the subjects' identity and the subjects' information. No medical records will be accessed at any point (before, during or after the study).

**Attachments**

Attach Type	File Name
Advertising	Advertising Flyer MOD1 10.17.2023-STAMPED.pdf
Advertising	[name] Email.png
Advertising	CC-OD-24-5681.pdf

**Research Procedures**

Describe how the research will be conducted.

- What experience will study participants have?
- What will study participants be expected to do?
- How long will the study last?
- Outline the schedule and timing of study procedures.
- Provide visit-by-visit listing of all procedures that will take place.
- Identify all procedures that will be carried out with each group of participants.
- Describe deception and debrief procedures if deception is involved.

Differentiate between procedures that involve standard/routine clinical care and those that will be performed specifically for this research project. List medications that are explicitly forbidden or permitted during study participation.

On day one of the study, following informed consent, we will perform baseline assessments including breath alcohol level, alcohol craving questionnaire, alcohol attentional bias tasks using eye tracker, and collection of baseline demographics. All of these baseline assessments will take a total of three hours. We will evaluate for any contraindications for MRI using the MRI checklist (attached). We will also obtain resting and active motor threshold from the first dorsal interosseous (FDI) muscle. Following this subjects will be transported to Magnetic Resonance Imaging and Spectroscopy Center (MRISC), affiliated with University of Kentucky for collection of their baseline MRI brain scan that will last thirty minutes. A study team member will escort them to the MRISC and will be with them when the scan is obtained.

On the second day, subjects will receive two sessions of active cTBS. Sessions will be the same in dosing and will be delivered at an interval of fifty minutes. Each session will last five minutes regardless of it being cTBS or sham cTBS. Active cTBS sessions will be delivered 120% resting motor threshold (RMT) to the left dorsolateral prefrontal cortex using a figure 8 coil and MagVenture MagPro x100 device (MagVenture A/S, Denmark), with TMS coil position stabilized using BrainSight (Rogue Solutions, Montreal, Canada). Subjects will also perform a host of other tasks as shown in figure 1 before and after the two cTBS sessions. At the end of the cTBS sessions and tasks, post session MRI brain scan will be collected at MRISC.

On day three of the study, participants will receive two sessions of sham cTBS. The sham cTBS mimics the actual experimental one but does not deliver any electricity to the brain. The sham sessions will be separated by 50 minutes. Participants will perform a host of other tasks as shown in figure 1 before and after the two sham cTBS sessions. At the end of day three, we will have participants undergo an MRI brain scan at MRISC.

A medical doctor will be present or nearby during all stimulation sessions. No drug, pregnancy, etc. screening results will be obtained from a UK HealthCare laboratory.

**Attentional Bias task**

We will have participants perform an attentional bias task. They will view alcohol and neutral cues presented side by side for 2 seconds. We will measure attentional bias using a Tobii Pro Fusion 120 Hz eye tracker (Tobii Technology, Sweden) eye tracker. Eye tracking will record eye movements and fixation times for both cue types. Upon offset of the cues, a visual probe ('X') will appear on either the left or right side of the computer screen. The primary dependent variable will be mean fixation time (milliseconds) calculated by summing the total fixation time for each cue type and then dividing by the total number of critical trials (i.e., 40).

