**Study Population:**

Describe the characteristics of the subject population, including age range, gender, ethnic background and health status. Identify the criteria for inclusion and exclusion.

Provide the following information:

- A description of the subject selection criteria and rationale for selection in terms of the scientific objectives and proposed study design;
- A compelling rationale for proposed exclusion of any sex/gender or racial/ethnic group;
- Justification for the inclusion of vulnerable groups such as children, prisoners, adults with impaired consent capacity, or others who may be vulnerable to coercion or undue influence.

Please consider these resources:

[NIH Diversity Policy](#)

[FDA Diversity Guidance](#) 

Inclusion criteria. Potential participants will be: 1) Patients seen at a clinic within the University of Kentucky Healthcare; 2) 21-60 years of age; 3) male or female gender 4) Able to read, understand and communicate in English; 5) willing to adhere to the general rules of the UK Healthcare; 6) Must fulfill DSM criteria for moderate alcohol use disorder.

Exclusion criteria. Positive pregnancy test for females, traumatic brain injury, history of seizure disorder, history of or current diagnosis of schizophrenia, intracranial metal shrapnel, previous adverse effect with TMS, sub-threshold consistency while performing behavioral tasks, failure to show baseline attentional bias to alcohol versus neutral cues.

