#### Data and Safety Monitoring

The IRB requires review and approval of data and safety monitoring plans for greater than minimal risk research or NIH-funded/FDA-regulated clinical investigations.

- If you are conducting greater than minimal risk research, or your clinical investigation is NIH-funded, describe your Data and Safety Monitoring Plan (DSMP). [Click here for additional guidance on developing a Data and Safety Monitoring Plan](#).
- If this is a non-sponsored investigator-initiated protocol considered greater than minimal risk research, and if you are planning on using a Data and Safety Monitoring Board (DSMB) as part of your DSMP, [click here for additional guidance](#) for information to include with your IRB application.

We will monitor the safety of participants, i.e., potential adverse events resulting from participation; and have procedures to safeguard against adverse events. We will actively screen and exclude any potential participants with a history of seizure disorder. We will also monitor every study session with a physician on site for every stimulation session. In case a seizure were to occur, having a physician on site in the room with the participant will help us in managing the event. All staff will also be trained in how to provide first aid in the event of a seizure ie lay the participant on their side and move any objects that can cause harm out of their vicinity.

We will also monitor for side effects after every stimulation session including headaches and neck pain. We will actively exclude participants with metal implants or piercings so that no adverse events occur during the MRI scan.

We will assure data accuracy and protocol compliance, including quality-control procedures in place to assure data accuracy and completeness. Appropriate procedures range, for example, from regular data verification and protocol compliance checks performed by a data manager and a principal investigator, to a formal external data audit process by an external agent.

[Back to Top](#)

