### Statistical analysis plan

We will calculate the mean and standard deviation values for PACS scores and alcohol cue attentional bias values for two time points (baseline and following the second session). This will be done across both cTBS and sham cTBS sessions. We will compare changes in these outcome measures across cTBS and sham cTBS sessions using t-tests.

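### The primary eye-tracking score divides by a fixed 40 trials, so trials without usable gaze shrink it; it should average over valid trials and state the bias formula

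*Combined protocol and SAP*

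**What the plan says.** The Attentional Bias task section shows the cues in pairs: "They will view alcohol and neutral cues presented side by side for 2 seconds". It adds: "Eye tracking will record eye movements and fixation times for both cue types". The outcome is then named: "The primary dependent variable will be mean fixation time (milliseconds"). The scoring rule for that outcome says it is to be "calculated by summing the total fixation time for each cue type and then dividing by the total number of critical trials (i.e., 40"). This gives two means per run, one for each cue type, each divided by 40.

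The SAP analyses one quantity, "alcohol cue attentional bias values for two time points (baseline and following the second session"), and compares its change between active and sham with t-tests. It gives no formula for turning the two means into that value. The exclusion criteria list "failure to show baseline attentional bias to alcohol versus neutral cues", which points to a contrast between cue types but is not a scoring rule.

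On data quality, the Data and Safety Monitoring section promises "quality-control procedures in place to assure data accuracy and completeness" in general terms. The Eye Tracker text under Resources says the device loses little data but gives no figure. The consistency criterion under Study Population removes participants, not trials. None of these changes the divisor.

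**The concern.** If the eye tracker records no usable gaze on a trial, that trial adds 0 ms to the sum but still counts among the 40. A missing measurement is then scored as if the participant had looked at neither cue. The score mixes where people looked with how well they were tracked.

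The outcome is described as primary, and Subject Info To-Date puts total enrolment at 8. All participants receive active stimulation first and sham a week later, so any drift in tracking quality between those days would not cancel through order. Greater loss after active cTBS would lower the score there, which is the direction of the hypothesised decrease.

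**Working it through.** **Inputs from the documents:** divisor 40; cue display 2 s, so alcohol plus neutral fixation cannot exceed 2,000 ms per trial; eye tracker at 120 Hz; 8 enrolled; the task performed before and after the sessions on each stimulation day, giving four runs. The documents give no fixation times, loss rate, SD, alpha or power calculation, so there is no stated figure to reproduce.

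**Assumptions:** true per-trial means A (alcohol) and N (neutral) of 800/700, 1000/700 or 1200/400 ms; SD of the paired contrast 100 ms (range 60 to 150), with the same SD used for every score for lack of a figure; two-sided 5% paired t-test.

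**1. Scaling.** With v tracked trials, the alcohol mean is A·v/40, the neutral mean N·v/40 and the difference (A−N)·v/40. The factor is 38/40 = 0.95 or 36/40 = 0.90. With 800/700 ms and v = 36, the totals are 36×800 = 28,800 and 36×700 = 25,200 ms.
- Divided by 40: (28,800−25,200)/40 = 90 ms.
- Divided by 36: (28,800−25,200)/36 = 100 ms.
- Proportion on alcohol: 28,800/(28,800+25,200) = 0.533 with either divisor.

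**2. Equal loss in all runs.** Multiplying every contrast by one constant scales its mean and SD alike, so t and p do not change. Only the millisecond estimate shrinks.

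**3. Loss varying at random between runs.** If the lost share has SD s, independently in four runs, the SD it adds to the contrast is √4·s·level. For s = 0.10:
- Difference, 100 ms gap: 2×0.10×100 = 20, and √(100²+20²) = 102.0 ms.
- Difference, 300 ms gap: 2×0.10×300 = 60, and √(100²+60²) = 116.6 ms.
- Alcohol alone at 800 ms: 2×0.10×800 = 160, and √(100²+160²) = 188.7 ms.

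This costs precision. Without an active-sham difference in loss, the simulated false-positive rate stays at about 5%.

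**4. Extra loss f after active only.** The spurious shift is f·(A−N) for the difference and f·A for alcohol alone. The noncentrality is (shift/SD)·√8 on 7 degrees of freedom. At f = 0.10 (4 of 40 trials):

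| A/N (ms) | Gap (ms) | Shift in difference (ms) | False-positive rate, SD 100 | SD 150 to SD 60 |
|---|---|---|---|---|
| 800/700 | 100 | 10 | 5.7% | 5.3% to 7.0% |
| 1000/700 | 300 | 30 | 11.4% | 7.8% to 23.2% |
| 1200/400 | 800 | 80 | 49.6% | 25.7% to 89.6% |

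For alcohol alone at A = 800, the shift is also 80 ms and the rate is again 49.6% at SD 100. With the SD of 188.7 ms from step 3, it falls to about 18%. In milliseconds, the alcohol-alone shift is A/(A−N) times the difference shift: 8, 3.3 and 1.5 times in the three rows.

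**5. Check by simulation.** A run of 2,000 trials per case at n = 8 assumed a mean of 36 tracked trials, falling to 32 after active only, and noisier data (contrast SD about 170 to 190 ms). The difference score divided by 40 had false-positive rates of 0.05, 0.07 and 0.17 for gaps of 100, 300 and 800 ms. Divided by tracked trials, the rate was about 0.05 in all three.

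**6. Loss within trials.** A 2 s window at 120 Hz holds 240 samples. If 10% are lost in every trial, all 40 trials may still count as valid, yet 800/700 becomes 720/630 and the difference 90 ms. A trial divisor does not repair this. The proportion does: 720/(720+630) = 0.533.

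**The case against.** The strongest reply is that 40 is the design count of critical trials. The text never says that untracked trials stay in as zeros, and an analyst might drop them. That is fair. What stands is that the written rule has a fixed divisor and no passage tells anyone to change it.

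Second, harm to the comparison needs loss that differs between post-active and post-sham runs, and the documents suggest none. The Study Design section states: "The same sequence of events will occur on day three of the study". The device is described as losing little data. A reader might infer that the divisor biases this trial towards finding an effect; the documents do not support that. Equally, matching procedures and an unquantified device description do not rule it out.

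Third, the objectives, the exclusion wording and the recording of both cue types make alcohol minus neutral the natural score. A reader might therefore infer that the problem is negligible for the difference and serious only for alcohol alone. That does not follow. Both scores shrink by the same proportion, and the difference shifts with a gap the documents do not report. It is modest at 100 ms and equals the alcohol-alone shift of the first row at 800 ms. The high alcohol-alone rates also assume identical extra loss in every participant.

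**Conclusion.** The point holds as a scoring weakness worth correcting, not as a demonstrated bias. Two consequences are certain if the rule is applied literally and any trials are lost: the millisecond estimate shrinks by v/40 and, where loss varies between runs, noise is added. Bias in the active-sham contrast is possible but not shown. At 10% extra loss after active only, it ranges from trivial (5.7%) to severe (49.6%) over assumed gaps of 100 to 800 ms at SD 100 ms. Those rates rest on assumed fixation times, SD and loss. The missing bias formula alone would be a gap in detail; it matters here because a difference, a proportion and an alcohol-only mean respond differently to lost trials.

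**What to change.** In the Attentional Bias task section and the SAP:

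- Define the bias value as mean alcohol-cue minus mean neutral-cue fixation time.
- Average each mean over the trials with valid gaze in that run, instead of over 40. Keep as valid any tracked trial in which the participant looked at neither cue, since that is a true zero.
- Before scoring, fix the share of the 240 samples a valid trial needs and a lenient minimum number of valid trials per run.
- Tabulate valid trials and usable-sample share by day and time point, so that any active-sham difference in loss is visible.
- Report alcohol/(alcohol+neutral) as a sensitivity analysis. It is unaffected by loss unrelated to cue type, including loss within trials.

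The cost is wording and rescoring, with no new data collection. It requires per-trial gaze validity to have been retained, which the documents do not confirm. Sparse runs may be noisier or dropped: going from 8 participants to 7 or 6 raises the paired effect detectable with 80% power from 1.16 SD to 1.27 or 1.43 SD, hence the lenient minimum. The Progress of the Research section says only data analyses remain, so the change must be labelled post hoc if scoring has begun.
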